6.5.4 Baseline Visit

The Baseline visit occurs between 14 to 31 days after the screening visit, depending on the required washout period following discontinuation of excluded therapies. Eligibility must be confirmed prior to randomization. At the Baseline visit, the following procedures and assessments are to be performed, preferably in the order shown below:

- Ask the subject to complete the DLQI, HADS, and ESS questionnaires
- Assess and record any changes in the subject's concomitant medications
- Assess and record any changes in the subject's medical history
 - Female subjects should be queried regarding history of, or current, breast masses or abnormal discharge, and history of mammography (if applicable), and history of abnormal vaginal bleeding or discharge
- Review menstrual diary and record dates of menstrual flow (if applicable)
- Assess AE's and record SAEs caused by protocol-mandated interventions
- Obtain vital signs
- Perform a urine pregnancy test for females of childbearing potential and confirm the subject has a negative urine pregnancy test result prior to randomization (with positive or equivocal results confirmed by a serum pregnancy test)
- Confirm subject's eligibility based on the inclusion/exclusion criteria (to include review of eDiary compliance for eligibility)
- Randomize subject in IWRS if eligibility confirmed
- Perform targeted physical examination, including weight
- Perform IGA PN-A
- Perform IGA PN-S
- Obtain photos (at selected sites, only subjects that signed photography consent)
- Dispense study drug; subjects will take loading dose of 3 tablets while on site
- Review eDiary for compliance, re-train subject as needed
- Assess and record any post-dose AEs and SAEs
- Confirm next scheduled visit

6.5.5 *Week 1 Telephone Contact Visit*

The Week 1 visit is a telephone visit that occurs 7 days (\pm 3 days) after the Baseline visit. At the Week 1 visit, the following procedures and assessments are to be performed:

- Assess and record any changes in the subject's concomitant medications
- Assess and record any AEs and SAEs
- Review eDiary for compliance, re-train subject as needed
- Confirm next scheduled visit

6.5.6 *Week 2 Visit*

The Week 2 visit occurs 14 days (\pm 3 days) after the Baseline visit. At the Week 2 visit, the following procedures and assessments are to be performed:

- Assess and record any changes in the subject's concomitant medications

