6.1.3 Visit Windowing

Data will be summarized based on nominal visit indications. Data collected during post-treatment follow-up will be summarized as

Protocol Version(s)	Nominal Visit	Analysis Visit
V2.0; V2.1	3-Week Follow-up	3-Week Follow-up
V2.0; V2.1	5-Week Follow-up	5-Week Follow-up

In addition, a “Latest Follow-up” visit will be summarized, which will include the latest available follow-up information for each subject from the 3-, 5- Week Follow-up visits.

Information collected at early treatment discontinuation visits will be mapped to the most appropriate visit based on the midpoints between scheduled visits.

For example, if a subject terminates use of study drug on or after Day 22 but before Day 36, data collected at the early end of treatment visit will be mapped to the Week 4 evaluation for summaries. If the subject has Week 4 values present, the data collected at the early end of

treatment visit will not replace the data collected at Week 4. For the sensitivity efficacy analyses, last observation carried forward (LOCF) will be applied subsequent to mapping the information to the appropriate visit.

Additionally, WI-NRS will be summarized at Weeks 1, 2, 3, 4, 5, 6, 7, 8, 9, 10 and 3- and 5-Week Follow-up by averaging the daily results for the 7 days prior to each week. The weekly average values will be calculated if a subject has at least four responses during the 7 day range, as defined below:

Week/Visit	Study Day Range
Week 1	2-7 (as Day 1 may be pre or post first dose)
Week 2	8-14
Week 3	15-21
Week 4	22-28
Week 5	29-35
Week 6	36-42
Week 7	43-49
Week 8	50-56
Week 9	57-63
Week 10	64-70
3-Week Follow-up	Post-treatment days 15-21
5-Week Follow-up	Post-treatment days 29-35

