Mean	xx.x	xx.x
SD	xx.xx	xx.xx
Median	xx.x	xx.x
Min. to Max.	xx to xx	xx to xx
Absolute Change from Baseline		
n	xx	xx
Mean	xx.x	xx.x
SD	xx.xx	xx.xx
Median	xx.x	xx.x
Min. to Max.	xx to xx	xx to xx

Note: No imputation of missing values. Baseline is the latest recorded value prior to first dose of study drug. Change calculated as post-baseline – baseline.

“Latest Follow-up” visit includes the latest available follow-up information for each subject from the 3-Week or 5-Week Follow-up visits.

SOURCE: USERNAME/SPONSOR/PROJECT/JOBNAME (DATE,TIME)

Table to include post-baseline visits of “Week 2”, “Week 10”, “3-Week Follow-up”, “5-Week Follow-up”, “Latest Follow-up”.

Table to include following lab tests: “BASOPHILS”, “EOSINOPHILS”, “HCT”, “HGB”, “LYMPHOCYTES”, “MCH”, “MCHC”, “MCV”, “MONOCYTES”, “NEUTROPHILS”, “PLATELET COUNT”, “RBC”, “WBC”.

CONFIDENTIAL

Table 14.3.1.4.1.2: Shift Summary of Hematology Laboratory Results
(Safety Population)
(Page 1 of xx)

<Test Name> (<units>)	Placebo (N=xxx)			Serlopitant 5 mg (N=xxx)		
		Week 2			Week 2	
Baseline	BNL	WNL	ANL	BNL	WNL	ANL
BNL	xx (xx.x%)	xx (xx.x%)	xx (xx.x%)	xx (xx.x%)	xx (xx.x%)	xx (xx.x%)
WNL	xx (xx.x%)	xx (xx.x%)	xx (xx.x%)	xx (xx.x%)	xx (xx.x%)	xx (xx.x%)
ANL	xx (xx.x%)	xx (xx.x%)	xx (xx.x%)	xx (xx.x%)	xx (xx.x%)	xx (xx.x%)
	Week 10			Week 10		
Baseline	BNL	WNL	ANL	BNL	WNL	ANL
BNL	xx (xx.x%)	xx (xx.x%)	xx (xx.x%)	xx (xx.x%)	xx (xx.x%)	xx (xx.x%)
WNL	xx (xx.x%)	xx (xx.x%)	xx (xx.x%)	xx (xx.x%)	xx (xx.x%)	xx (xx.x%)
ANL	xx (xx.x%)	xx (xx.x%)	xx (xx.x%)	xx (xx.x%)	xx (xx.x%)	xx (xx.x%)
	3-Week Follow-up			3-Week Follow-up		
Baseline	BNL	WNL	ANL	BNL	WNL	ANL
BNL	xx (xx.x%)	xx (xx.x%)	xx (xx.x%)	xx (xx.x%)	xx (xx.x%)	xx (xx.x%)
WNL	xx (xx.x%)	xx (xx.x%)	xx (xx.x%)	xx (xx.x%)	xx (xx.x%)	xx (xx.x%)
ANL	xx (xx.x%)	xx (xx.x%)	xx (xx.x%)	xx (xx.x%)	xx (xx.x%)	xx (xx.x%)
	5-Week Follow-up			5-Week Follow-up		
Baseline	BNL	WNL	ANL	BNL	WNL	ANL
BNL	xx (xx.x%)	xx (xx.x%)	xx (xx.x%)	xx (xx.x%)	xx (xx.x%)	xx (xx.x%)
WNL	xx (xx.x%)	xx (xx.x%)	xx (xx.x%)	xx (xx.x%)	xx (xx.x%)	xx (xx.x%)
ANL	xx (xx.x%)	xx (xx.x%)	xx (xx.x%)	xx (xx.x%)	xx (xx.x%)	xx (xx.x%)
	Latest Follow-up			Latest Follow-up		
Baseline	BNL	WNL	ANL	BNL	WNL	ANL

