 “Latest Follow-up” visit includes the latest available follow-up information for each subject from the 3-Week or 5-Week Follow-up visits.
 SOURCE: USERNAME\SPONSOR\PROJECT\JOBNAME (DATE,TIME)

Table to include post-baseline visits of “Week 10”, “3-Week Follow-up”, “5-Week Follow-up”, “Latest Follow-up”.

Table to include following lab tests: “TSH ULTRASENSITIVE”, “THYROXINE, FREE”, “CORTISOL, SERUM RANDOM”, “ACTH, PLASMA”, “ANTI-MULLERIAN HORMONE”, “FSH”, “ESTRADIOL”, “LUTEINIZING HORMONE”, “PROGESTERONE”.

CONFIDENTIAL

Table 14.3.1.4.3.1.2: Summary of Reproductive Endocrine Laboratory Results
 (Safety Population – Females Using Hormonal Contraception/Therapy)
 (Page 1 of xx)

<Test Name> (<units>)	Placebo (N=xxx)	Serlopitant 5 mg (N=xxx)
Baseline		
n	xx	xx
Mean	xx.x	xx.x
SD	xx.xx	xx.xx
Median	xx.x	xx.x
Min. to Max.	xx to xx	xx to xx
Week 10		
n	xx	xx
Mean	xx.x	xx.x
SD	xx.xx	xx.xx
Median	xx.x	xx.x
Min. to Max.	xx to xx	xx to xx
Absolute Change from Baseline		
n	xx	xx
Mean	xx.x	xx.x
SD	xx.xx	xx.xx
Median	xx.x	xx.x
Min. to Max.	xx to xx	xx to xx

Note: No imputation of missing values. Baseline is the latest recorded value prior to first dose of study drug. Change calculated as post-baseline – baseline.
 “Latest Follow-up” visit includes the latest available follow-up information for each subject from the 3-Week or 5-Week Follow-up visits.
 SOURCE: USERNAME\SPONSOR\PROJECT\JOBNAME (DATE,TIME)

Table to include post-baseline visits of “Week 10”, “3-Week Follow-up”, “5-Week Follow-up”, “Latest Follow-up”.

Table to include following lab tests: “ANTI-MULLERIAN HORMONE”, “FSH”, “ESTRADIOL”, “LUTEINIZING HORMONE”, “PROGESTERONE”.

CONFIDENTIAL

Table 14.3.1.4.3.1.3: Summary of Reproductive Endocrine Laboratory Results
(Safety Population – Females Not Using Hormonal Contraception/Therapy)
(Page 1 of xx)

<Test Name> (<units>)	Placebo (N=xxx)	Serlopitant 5 mg (N=xxx)
Baseline		
n	xx	xx
Mean	xx.x	xx.x
SD	xx.xx	xx.xx
Median	xx.x	xx.x
Min. to Max.	xx to xx	xx to xx
Week 10		
n	xx	xx
Mean	xx.x	xx.x
SD	xx.xx	xx.xx
Median	xx.x	xx.x
Min. to Max.	xx to xx	xx to xx
Absolute Change from Baseline		
n	xx	xx
Mean	xx.x	xx.x
SD	xx.xx	xx.xx
Median	xx.x	xx.x
Min. to Max.	xx to xx	xx to xx

Note: No imputation of missing values. Baseline is the latest recorded value prior to first dose of study drug. Change calculated as post-baseline – baseline.

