Table to include parameters in following order: “Temperature (degrees Celsius)”, “Respiration Rate (breaths/min)”, “Heart Rate (beats/min)”, “Systolic Blood Pressure (mmHg)”, “Diastolic Blood Pressure (mmHg)”.

Table to include post-baseline visits of “Week 2”, “Week 4”, “Week 6”, “Week 10”, “3-Week Follow-up”, “5-Week Follow-up”, “Latest Follow-up”.

Table 14.3.1.7.1: Summary of Hospital Anxiety and Depression Scale (HADS)
(Safety Population)
(Page 1 of xx)

<Subscale>	Placebo (N=xxx)	Serlopitant 5 mg (N=xxx)
Baseline		
n	xx	xx
Mean	xx.x	xx.x
SD	xx.xx	xx.xx
Median	xx.x	xx.x
Min. to Max.	xx to xx	xx to xx
Week 4		
n	xx	xx
Mean	xx.x	xx.x
SD	xx.xx	xx.xx
Median	xx.x	xx.x
Min. to Max.	xx to xx	xx to xx
Absolute Change from Baseline		
n	xx	xx
Mean	xx.x	xx.x
SD	xx.xx	xx.xx
Median	xx.x	xx.x
Min. to Max.	xx to xx	xx to xx

Note: Baseline is the latest recorded value prior to first dose of study drug. Change calculated as post-baseline – baseline. “Latest Follow-up” visit includes the latest available follow-up information for each subject from the 3-Week or 5-Week Follow-up visits.

SOURCE: USERNAME\SPONSOR\PROJECT\JOBNAME (DATE,TIME)

Table to include subscales in following order: “Anxiety Subscale”, “Depression Subscale”.

Table to include post-baseline visits of “Week 4”, “Week 10”, “3-Week Follow-up”, “5-Week Follow-up”, “Latest Follow-up”.

Table 14.3.1.8.1: Summary of Epworth Sleepiness Scale (ESS)
(Safety Population)
(Page 1 of xx)

	Placebo (N=xxx)	Serlopitant 5 mg (N=xxx)
ESS		
Baseline		
n	xx	xx
Mean	xx.x	xx.x
SD	xx.xx	xx.xx
Median	xx.x	xx.x
Min. to Max.	xx to xx	xx to xx
Week 4		
n	xx	xx
Mean	xx.x	xx.x
SD	xx.xx	xx.xx
Median	xx.x	xx.x
Min. to Max.	xx to xx	xx to xx
Absolute Change from Baseline		
n	xx	xx
Mean	xx.x	xx.x
SD	xx.xx	xx.xx
Median	xx.x	xx.x
Min. to Max.	xx to xx	xx to xx

Note: Baseline is the latest recorded value prior to first dose of study drug. Change calculated as post-baseline – baseline. “Latest Follow-up” visit includes the latest available follow-up information for each subject from the 3-Week or 5-Week Follow-up visits.

SOURCE: USERNAME\SPONSOR\PROJECT\JOBNAME (DATE,TIME)

Table to include post-baseline visits of “Week 4”, “Week 10”, “3-Week Follow-up”, “5-Week Follow-up”, “Latest Follow-up”.

CONFIDENTIAL

Table 14.3.1.9: Summary of Pharmacokinetic Concentrations
(Safety Population)

<Analyte> (<units>)	Placebo (N=xxx)	Serlopitant 5 mg (N=xxx)
Week 2		
n	xx	xx
Mean	xx.x	xx.x
SD	xx.xx	xx.xx
Median	xx.x	xx.x

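### The SAP maps early-discontinuation data to visits that the laboratory, HADS/ESS and by-visit ECG tables do not show, so the last on-drug reading of some early stoppers drops out of the between-arm summaries

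*SAP*

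**What the plan says.** SAP 6.1.3 (Visit Windowing) has one mapping rule for everything collected at an early treatment discontinuation visit: "Information collected at early treatment discontinuation visits will be mapped to the most appropriate visit based on the midpoints between scheduled visits". Its example is a subject who "terminates use of study drug on or after Day 22 but before Day 36", whose data go to Week 4. A no-replacement condition follows: if Week 4 values exist, data from the early end of "treatment visit will not replace the data collected at Week 4".

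Protocol Appendix A, Table 2, marks Labs, HADS/ESS, ECG and vital signs at the Early Treatment Discontinuation visit, so these data are collected.

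The shells in SAP section 10 name the on-treatment visits to be tabulated:

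- Hematology and chemistry: "Table to include post-baseline visits of “Week 2”, “Week 10", then follow-up. The shift tables use the same visits.
- Endocrine: "Table to include post-baseline visits of “Week 10”, “3-Week Follow-up" and later follow-up.
- HADS and ESS: "Table to include post-baseline visits of “Week 4”, “Week 10", then follow-up.
- ECG parameters and the ECG shift table: Weeks 2, 4 and 10, then follow-up.
- Vital signs: Weeks 2, 4, 6 and 10, then follow-up.

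No laboratory, HADS/ESS or by-visit ECG shell has an end-of-treatment, last-on-drug or worst-value row. Latest Follow-up draws only on the 3- and 5-week follow-up visits.

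**The concern.** A mapping rule built on all clinic visits is paired with tables that show only the visits at which each test is scheduled. A subject who stops on Day 40 has laboratory, HADS/ESS and ECG data sent to Week 6, and no table for those assessments has a Week 6 row.

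Changes from baseline in laboratory parameters, ECG, HADS and ESS are named safety endpoints (SAP 5.2). Protocol 5.6 lists abnormal thyroid, prolactin, cortisol or corticotropin results among possible reasons to stop study drug, so early stopping may itself carry safety information. The reading closest to the last dose in these subjects should be compared between arms, and the by-visit tables as specified would not do so.

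**Working it through.** **Visit days.** Protocol 6.5.6 says "The Week 2 visit occurs 14 days" after Baseline, and sections 6.5.7 to 6.5.9 give 28, 42 and 70 days. With Baseline as Day 1, the visits fall on Days 15, 29, 43 and 71.

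**Reproducing the SAP's own figure.** The example window for Week 4 is "on or after Day 22 but before Day 36".

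- (15 + 29)/2 = 22 and (29 + 43)/2 = 36, an exact match.
- If Week 6 were not counted, the upper bound would be (29 + 71)/2 = 50, which is not the SAP's figure.

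The other midpoints are (1 + 15)/2 = 8 and (43 + 71)/2 = 57. The windows are therefore Days 8-21 to Week 2, Days 22-35 to Week 4, Days 36-56 to Week 6, and Day 57 onward to Week 10. The rule does not say whether Days 1-7 go to Baseline or Week 2.

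**Stop days (of 70) with no row in the tables.**

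| Assessment | On-treatment rows | Stop days without a row | Share |
|---|---|---|---|
| Hematology, chemistry | Weeks 2, 10 | 22-56 | 35/70 = 50% |
| HADS, ESS | Weeks 4, 10 | 8-21 and 36-56 | (14 + 21)/70 = 50% |
| HADS, ESS, with Days 1-7 | Weeks 4, 10 | 1-21 and 36-56 | 42/70 = 60% |
| ECG by visit | Weeks 2, 4, 10 | 36-56 | 21/70 = 30% |
| Vital signs | Weeks 2, 4, 6, 10 | none | 0% |

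Days 1-7 are taken as Week 2 for laboratory tests, ECG and vital signs, which favours the plan.

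**Adding the no-replacement condition.** Assume each scheduled visit was attended on its nominal day. A later stop in the same window then loses its end-of-treatment value.

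- Hematology and chemistry lose Days 16-21 as well: (35 + 6)/70 = 59%.
- HADS/ESS lose Days 30-35: (35 + 6)/70 = 59%, or (42 + 6)/70 = 69% with Days 1-7.
- ECG loses Days 16-21 and 30-35: (21 + 12)/70 = 47%.

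**What the affected subjects still have in the tables.**

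- Hematology and chemistry stops on Days 22-56 come after the Week 2 draw.
- ECG stops on Days 36-56 come after Weeks 2 and 4.
- HADS/ESS stops on Days 36-56 come after Week 4. Stops on Days 8-21 do not, so for 14 of the 35 days the early-discontinuation value is the only on-drug HADS/ESS value.

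**Illustration only.** Assume 10-20% stop early, evenly over Days 1-70. Of 140 per arm, 14-28 stop. The 50% share gives 7-14 per arm for hematology and chemistry and the same for HADS/ESS; the 30% share gives about 4-8 for ECG. The nearest figure in the documents is TCP-102, where 9 of 128 (7.0%) discontinued for TEAEs over 8 weeks. That rate gives 280 × 0.070 ≈ 20 subjects, about 10 of them in the 50% window across both arms. It counts adverse-event stops only.

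**The case against.** **The rule may be meant per assessment.** The text says most appropriate visit, and the example fits vital signs, which are taken and tabulated at Week 6. That reading is not excluded, but the SAP does not state it, and the example's upper bound does not fit it for laboratory tests, HADS/ESS or ECG. Nor would it be a full repair. Laboratory data would split at (15 + 71)/2 = Day 43, and no-replacement would still drop stops on Days 16-42 (27/70 = 39%). HADS/ESS would split at (29 + 71)/2 = Day 50 and lose Days 30-49 (20/70 = 29%).

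**The values are not lost to the report.** This stands. They appear in by-subject listings, clinically significant abnormalities are recorded as AEs (Protocol 7.1.3), and Table 14.3.1.5.1.1 summarises treatment-emergent ECG abnormalities across visits. SAP 6.9.3 also promises a summary of out-of-range laboratory values at any post-baseline assessment, but the index holds only by-visit summary and shift tables and a listing. That summary would not cover HADS/ESS or mean changes.

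**Early stoppers left with off-drug data only.** A reader might infer this, since follow-up comes 5 weeks after the last dose: 840 h, or 9.8 to 18.7 half-lives at 86 to 45 h. The documents do not support it in general, because most affected subjects have an earlier on-drug value in the tables. HADS/ESS stops before Week 4 are the exception.

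**An 80% endocrine loss.** This is also tempting: stops before Day 57 are 56/70. But Protocol 6.2.3 and Table 2 footnote 5 name only Screening, Week 10 and Follow-up as endocrine visits. The general Labs mark at early discontinuation does not establish that endocrine tests are drawn there.

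**Conclusion.** The gap holds in a limited form. Under the windows that the SAP's example implies, the end-of-treatment value has no place in the by-visit tables for 50% of stop days for hematology and chemistry, 50-60% for HADS/ESS and 30% for ECG. No-replacement adds to each. The laboratory and ECG shift tables share the gap; HADS and ESS have no shift tables. What is usually lost from the arm comparison is the last on-drug reading.

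These are shares of stop days. They become shares of stoppers only if stopping is evenly spread, and the documents give neither rate nor timing, so it cannot be said that many subjects are affected. Endocrine values, if drawn at early discontinuation, would be tabulated only for stops from Day 57.

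A reader might also infer that the Week 10 tables lean toward no effect. The direction is not shown: in TCP-102, TEAE discontinuations were 3 on serlopitant and 6 on placebo. The tables are descriptive and the primary analysis is untouched. This is a cheap improvement worth making.

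**What to change.** Add to SAP 6.1.3 an End of Treatment analysis visit: the Week 10 value or, for early stoppers, the Early Treatment Discontinuation value, with no replacement restriction. Add that row or panel to:

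- the hematology and chemistry summary and shift tables (14.3.1.4.1.1-2 and 14.3.1.4.2.1-2);
- the by-visit ECG tables (14.3.1.5.1.2-3);
- the HADS and ESS tables (14.3.1.7.1 and 14.3.1.8.1);
- the endocrine tables (14.3.1.4.3.1.1-3 and 14.3.1.4.3.2), where early-discontinuation values exist.

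State whether midpoint mapping is specific to each assessment, and add to the index the out-of-range laboratory table promised in SAP 6.9.3. Mapping to the nearest visit at which the test is scheduled is not enough by itself, because no-replacement would still discard values.

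The cost is SAP wording, one extra row or panel per safety table and one new laboratory table. No new data are needed.

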Initiation or use of topical therapy with corticosteroids, calcineurin inhibitors, calcipotriene, PDE-4 inhibitors is not permitted within 4 weeks prior to the Baseline visit or throughout the treatment period, but such therapy may be initiated during the follow-up period if needed.

Initiation of bland emollient is not permitted within 2 weeks (14 days) prior to Baseline visit or throughout the treatment period, but such therapy may be initiated during the follow-up period if needed.

The following therapies and activities are excluded from the Screening visit through the treatment period, and through the follow-up period:

- NK₁-R antagonists (other than study drug)
- Systemic immunosuppressive/ immunomodulatory therapies (including but not limited to systemic corticosteroids, PDE-4 inhibitors, cyclosporine, mycophenolate-mofetil, methotrexate, azathioprine, thalidomide, interferon-gamma, or phototherapy)
- Biologic therapies (other than therapies such as insulins, vaccines)
- Strong CYP3A4 inhibitors (See [Appendix B](#))
- Use of an indoor tanning facility, or natural sun exposure resulting in significant tanning or sunburn
- Any investigational therapy

The following therapies and activities are excluded from the Screening visit through the treatment period, and use is discouraged, though permitted, through the follow-up period:

- Topical therapies or emollients with anti-pruritic properties (including but not limited to anti-histamines, menthol or menthol derivatives, polidocanol, camphor, pramoxine, and capsaicin)
- Systemic therapies with recognized anti-pruritic properties (including but not limited to H1 antihistamines, doxepin, gabapentin, pregabalin, cannabinoids, kappa-opioid receptor agonists, and mu-opioid receptor antagonists)

Use of any excluded therapies (including those for the treatment of pruritus or PN lesions, or as rescue therapy) should be reported as soon as possible, and will be recorded as protocol deviations for subjects who receive them.

5.7.3 *Rescue Therapies*

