- Perform targeted physical examination, including weight
- Assess and record any AEs and SAEs
- Collect returned study drug
- Utilize IWRS to assign new bottle of study drug
- Review eDiary for compliance, re-train subject as needed
- Confirm next scheduled visit

6.5.9 *Week 10 Visit*

The Week 10 visit occurs 70 days (± 7 days) after the Baseline visit. At the Week 10 visit, the following procedures and assessments are to be performed:

- Ask the subject to complete the DLQI, HADS, and ESS questionnaires
- Assess and record any changes in the subject's concomitant medications
- Female subjects should be queried for presence of new breast masses or abnormal discharge, and abnormal vaginal bleeding or discharge
- Review menstrual diary and record dates of menstrual flow (if applicable)
- Obtain ECG
- Obtain vital signs
- Perform targeted physical examination, including weight
- Perform IGA PN-A
- Perform IGA PN-S
- Perform a urine pregnancy test for females of childbearing potential (with positive or equivocal results confirmed by a serum pregnancy test)

- Draw blood for clinical laboratory tests (morning blood sampling due to Endocrine assessments)
 - Reproductive endocrine labs for females under 55 years of age at consent
 - Endocrine
 - Hematology
 - Chemistry
- Collect PK blood sample
- Assess and record any AEs and SAEs
- Collect returned study drug
- Obtain photos (at selected sites, only subjects that signed photography consent)
- Review eDiary for compliance, inform subject to continue entering WI-NRS score until Follow-up visit
- Review study drug compliance with re-training as required
- Confirm next scheduled visit date

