6.1.5 Handling of Dropouts or Missing Data

Should a determination of treatment period (on treatment, pre-treatment, post-treatment) be required for AEs or concomitant medication but the corresponding date is missing, or is a partial date, the event/medication will be considered on treatment unless the portions of the date that are available indicate this is not possible.

The primary method of handling missing efficacy data will be Markov Chain Monte Carlo (MCMC) multiple imputation. Imputation will be conducted within each treatment group independently, so the pattern of missing observations in one treatment group cannot influence missing value estimations in another. For each imputation process, 25 imputations will be performed.

Subjects that withdrew from the study due to lack of efficacy will have missing values imputed, however, the WI-NRS responder status will be defined as non-responder. Subjects that used an excluded therapy to treat worsening of pruritus or PN will have data values collected after the use of the excluded therapy set to missing and subsequently imputed. These subjects will also have the WI-NRS responder status defined as non-responder.

Missing WI-NRS data will be derived for the analysis using the method of MCMC multiple imputation. The 4-point responder status will be derived from imputed WI-NRS values. Since both primary and key secondary endpoints require WI-NRS, the following steps will be followed:

1. Using the daily eDiary data, calculate Baseline and Week 1 through Week 10 values by averaging available values. In order to compute a week's average, a minimum of 4 values must be available for that week. The weekly average will be imputed when there are fewer than 4 values available.
2. From step 1, create a dataset for each treatment group, of subjects with observed values and those needing estimation by MCMC. The missing WI-NRS values in each dataset will be filled in using the MCMC method to generate 25 datasets. The resulting datasets for each treatment group will be combined into one complete dataset.

Syntax:

```
proc mi data=datain out=dataout seed=&seed. Nimpute=25 <options>;
  where trtpn=(TRT); /* Note TRT = [1, 2]; depending on treatment group */;
  mcmc chain=single;
  var baseline week1 week2 week3 week4 week5 week6 week7 week8 week9
      week10;
run;
```

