6.7 Analysis of Efficacy

The efficacy endpoints will be summarized within the ITT and PP populations using descriptive statistics by time point and treatment. Available results including averaged imputed values, as well as change from baseline, will be summarized for each applicable time point. The WI-NRS and change from baseline will also be presented for each study day in a by-subject listing.

For the 4- and 3-point responder rate endpoints, subjects will be considered responders if they have at least a 4- / 3-point reduction between baseline and the corresponding week. Subjects that discontinued study drug due to lack of efficacy or used an excluded medication to treat worsening of pruritus or PN will be considered non-responders.

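### Does the primary endpoint need a stated cut-off day for therapy started in follow-up but still inside the Day 64-70 scoring window?

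*SAP*

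**What the plan says.** **Window.** SAP 6.1.3 obtains each weekly WI-NRS value "by averaging the daily results for the 7 days prior to each week". Week 10 is Study Days 64-70, with at least four entries and no on-treatment condition. Protocol 6.5.9 states: "The Week 10 visit occurs 70 days (± 7 days) after the Baseline visit". The diary continues to the Follow-up visit (Protocol 6.5.9; Appendix A, Table 3).

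**Therapies.** Protocol 5.7.2 works by period and class.
- Topical corticosteroids, calcineurin inhibitors, calcipotriene and PDE-4 inhibitors are barred before Baseline and "throughout the treatment period, but such therapy may be initiated during the follow-up period if needed".
- For topical and systemic anti-pruritics, "use is discouraged, though permitted, through the follow-up period".
- Systemic immunosuppressants, biologics and some others "are excluded from the Screening visit through the treatment period, and through the follow-up period".

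**Scoring.** SAP 6.1.5: "Subjects that used an excluded therapy to treat worsening of pruritus or PN will have data values collected after the use" set to missing and then imputed. It adds: "These subjects will also have the WI-NRS responder status defined as non-responder". SAP 6.7 repeats that those who "used an excluded medication to treat worsening of pruritus or PN will be considered non-responders", and applies the same to subjects who stop study drug for lack of efficacy. None of these sentences carries a date.

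**The concern.** A subject seen on Day 64 finishes treatment and starts a topical steroid for worsening on Day 65. If excluded means excluded at that time, the steroid is allowed and the relieved diary scores count toward response. If it means anything listed in Protocol 5.7.2, the subject is a non-responder. Two programmers could give one subject opposite primary outcomes, and settling the matter after unblinding would be a post-hoc choice on the primary endpoint.

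An early stopper who keeps the diary can have a Week 10 average made wholly of follow-up days. The rule also has no printed end. Read literally, a systemic immunosuppressant taken for worsening after Day 70 would overturn a response already observed.

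**Working it through.** **Plan's own figure.** The plan states 280 subjects (140 per arm) and more than 90% power, with the responder rates blacked out, so it cannot be reproduced. The concern does not rest on it. As an assumed scenario for scale, 25% vs 43.3% at 140 per arm gives 90.2% power (pooled chi-square, two-sided 5%).

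**1. Overlap of follow-up with Days 64-70.**
- Week 10 visit: 70 ± 7 days after Day 1, so Days 64-78.
- For a visit and last dose on Day *v*, follow-up days in the window = 70 − *v*: Day 64 gives 6, Day 67 gives 3, Day 70 gives 0.
- For an early stopper with last dose on Day *L* and 35 days of follow-up, four entries in the window need a diary to Day 67. So *L* ≥ 67 − 35 = 32, and Days 32-63 are 32 possible stop days.

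**2. Which reading do the documents support?**
- Protocol 5.7.3 discusses starting other therapy for worsening during the treatment period and refers the analysis of that use to Protocol 8.2. Protocol 8.2 holds the non-responder rule, with nearly the same trigger as SAP 6.1.5.
- Protocol 5.7.2 records use of an excluded therapy as a protocol deviation. Use that it permits in follow-up is not a deviation, so calling it excluded is the strained reading.
- SAP 6.1.5 already classes concomitant medication as pre-, on- or post-treatment, with a default for partial dates. SAP 6.9.1 already derives an end-of-treatment date. The analyst has both the period and the date.
- For use after Day 70, SAP 6.1.5 removes only values collected after the use, so the Week 10 scores stand. Overturning them follows only from reading the non-responder sentence alone.

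**3. How many responders could depend on the reading?**

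Early stoppers: the Phase 2 PN study (Protocol 1.5.3) had 3 serlopitant and 6 placebo stops for adverse events among 128, taken as 64 per arm.
- Scaled: 3/64 × 140 = 6.6 and 6/64 × 140 = 13.1.
- Stops spread evenly over 70 days (assumed): × 32/70 = 3.0 and 6.0.
- If 25-75% start a permitted therapy by Day 70 and 25-50% of users still show a 4-point fall (both assumed): 3.0 × 0.0625 to 0.375 = 0.2-1.1 serlopitant; 6.0 × the same = 0.4-2.3 placebo.

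Early attenders: if 5-25% of 280 attend on Days 64-69 and 0-10% of them start such a therapy by Day 70 (assumed), that is 14-70 subjects, of whom 0-7 start one. With 25-50% scoring a response, the ceiling of 7 becomes 1.75-3.5 responders across both arms.

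**4. Effect on the test** (unstratified pooled z, 140 per arm, assumed counts).

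| Placebo vs serlopitant responders | z | p |
|---|---|---|
| 35 vs 50 | 1.950 | 0.051 |
| 33 vs 50 | 2.225 | 0.026 |
| 35 vs 48 | 1.701 | 0.089 |
| 35 vs 61 (25% vs about 43.3%) | 3.273 | 0.0011 |
| 35 vs 59 | 3.037 | 0.0024 |

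Moving two responders in one arm matters only when the starting p-value is already close to 0.05.

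**5. Off-drug days alone.** Take effect as proportional to receptor occupancy *r*/(1 + *r*), with *r* = 0.94/0.06 = 15.7 from Protocol 3.2, or 12.5 after scaling by 4/5 for the capsule-tablet equivalence in Protocol 1.5.2. Let *r* decay with the 45-86 hour half-life in Protocol 1.5.1. With a visit-day dose and visits even over Days 64-69, the mean loss of effect is 2.1-6.3%. If 5-25% of subjects are such early attenders, power falls from 90.2% to 89.3-90.1%.

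**The case for a change.** The best case for a change is that the scoring rule decides primary-endpoint status and two or three sentences would date it, using medication dates and indications already collected. The class reading has some footing: the drugs appear under a heading of excluded therapies, and the SAP sentences are undated. The Per Protocol criteria in SAP 6.4.3 are limited to medication that could plausibly affect Week 10, whereas the responder rule has no such limit. The sponsor's approval before unblinding under SAP 6.4 covers analysis populations, not responder status. An undated rule could also let therapy on Day 40 overwrite Week 2 and Week 4 status, the two key secondary endpoints.

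The missing cut-off day stands, for Weeks 2 and 4 as well as Week 10, and so does the literal oddity for agents that stay excluded throughout follow-up. The claim that the Week 10 readings are evenly balanced does not stand, because it leaves out the link from Protocol 5.7.3 to 8.2. Nor is there one correct scoring to impose: counting permitted follow-up use as observed, or as failure, are both defensible if chosen blind. A sentence counting everything barred during treatment would reach too far, since Protocol 5.7.2 also bars starting a bland emollient in that period. A completer seen on Day 64 who began a moisturiser for worsening itch on Day 65 would become a primary-endpoint failure.

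The early-stopper route is narrower than it looks. Subjects who stop for lack of efficacy are already non-responders under SAP 6.7. Table 2 of Protocol Appendix A also marks diary collection at early discontinuation; if that is followed, Week 10 is missing and imputed. The early-visit route does not depend on this.

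**Conclusion.** No change to the plan follows. The fixed window is defined, treats both arms alike and suits an intent-to-treat analysis. What is absent is a printed cut-off day, and the protocol's period-based permissions and its placing of rescue in the treatment period point to a sensible default. An analyst would apply the rule to treatment-period use, leave observed values untouched by anything started after the scoring window closes, and record that convention at blinded data review.

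The size is small: at most about 1 serlopitant and 2 placebo responders from early stoppers and up to 3.5 across both arms from early attenders, direction unknown. Those ceilings rest on assumed uptake, response and attendance rates that the documents do not supply. The p-value shifts at 35 vs 50 are illustrations from a starting point chosen near 0.05. The verdict also assumes that the convention is fixed before unblinding; nothing in the documents suggests otherwise.
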